7.5.3 Other Safety Variables

Laboratory evaluations, vital signs, BMI, body weight, height, Investigator’s Global Assessment of Tolerability, and incidences of subjects with antibodies against BoNT-A will be analyzed descriptively (values and changes from baseline) and screened for individual notable values and/or changes. Results of the C-SSRS will be summarized descriptively.

The following analyses will be performed for the MP data:

C-SSRS

Additionally, to fulfill FDA requirements, prospective monitoring of suicidality with the C-SSRS should be considered the most important (but not the only) source of information concerning suicidality.

These C-SSRS assessments will be done in the subpopulation of subjects enrolled after amendment 1.0 approval only.

Suicidality will be assessed prospectively in subjects at baseline and all post-baseline visits. The appropriate version of this scale ensures the consistent application of this important measure regardless of indication or investigator experience with the subject matter. With C-SSRS in place, administration of this semi-structured clinician-based assessment scale is standardized. The C-SSRS quickly and efficiently identifies those subjects that require additional clinician follow up.

Following versions of the C-SSRS are to be applied only for subjects enrolled after amendment approval:

1. Children's baseline / screening version
2. Children's since last visit version.

The C-SSRS interview should only be assessed with children of respective age and cognitive state. Clear age cut-offs for the C-SSRS were not defined by the authors, but it has been found that administration is possible in general for children with a developmental age of about 7 years. Otherwise it should be documented in the eCRF that a child was not able to assess the C-SSRS at a respective visit.

The C-SSRS is based on the research and development at the Columbia University by Posner et al. [Posner 2007a (3)] supported by Columbia-Classification Algorithm for Suicide Assessment (C-CASA) developed by the same group [Posner 2007b (4)]. It is a semi-structured clinical interview consisting of domains of suicidal ideation, suicidal behavior and non-suicidal self-injurious behavior, and details of actual and potential lethality. It is designed for personal interview administration. Subjects or Parents/Caregivers are asked directly by a trained clinical assessor. Clinical assessment questions are presented, and subjects provide their responses. These responses enable the interviewer to branch to the appropriate follow up questions, faithfully adhering to C-SSRS probing specifications and potential positive responses. This approach provides consistent assessment and documentation.

At the end of the assessment the subject should not be released from the study center until the results of the C-SSRS (positive or negative) are reviewed and the subject is not considered to be at risk. If there is doubt about whether a subject is at risk, the Investigator should obtain appropriate psychiatric consultation.

For the sub-population of subjects enrolled after amendment approval and of respective age and cognitive state the following analysis will be performed. Descriptive frequency tables will be displayed for total sub-population and by treatment group. The number of subjects who experience any suicidal ideation, suicidal behavior, or self-injurious behavior without suicidal intent at least once at any post-baseline visit of the Main Period will be tabulated. Statistical evaluation of the data will be performed according to Table 1 of the Columbia–Suicide Severity Rating Scale Scoring and Data Analysis Guide Version 2.0 (Finalized February 2013) [Nilsson 2013 (5)]. Baseline data and further C-SSRS data such as intensity of ideation and lethality data will only be listed.

Laboratory data

Descriptive statistics for absolute values at Screening V1 will be given for continuous variables. No categorical laboratory variables will be collected. Laboratory parameters will be sorted by predefined categories (e.g., hematology, differential count, and chemistry).

Laboratory data, unscheduled and doubly performed laboratory data will be listed individually. For additionally performed laboratory measurements of certain subjects on other visit dates or of other laboratory parameters than planned no descriptive statistics will be created.

If subjects have additional laboratory examinations during screening examination, only the last sample before application of study medication will be used for final analysis tables. No post-baseline laboratory data is planned for the MP.

Vital signs, body weight, height, and BMI

The individual blood pressure, heart rate, body weight, height, and BMI data will be listed and summarised (n, mean, standard deviation, minimum, 1st quartile, median, 3rd quartile and maximum) at each time point. Descriptive statistics will be given for absolute values and changes from baseline V2.

Frequencies of subjects with lowered, normal, or raised values will be displayed as shift tables from Baseline V2 vs. Control Visits V3, V4, and Final Visit V5.

High and low values are defined as given in Table 4.

Table 4: High and Low Values of Vital Signs

Vital Sign Variable	Flag	Observed Value
Systolic Blood Pressure (mmHg)	High	≥ 180
	Low	≤ 90
Diastolic Blood Pressure (mmHg)	High	≥ 105

Vital Sign Variable	Flag	Observed Value
Heart rate (bpm)	Low	≤ 55
	High	≥ 110
Height (cm)	High	Not applicable
	Low	Not applicable
Weight (kg)	High	Not applicable
	Low	Not applicable
BMI (kg/cm ²)	High	≥ 30
	Low	≤ 18.5

A value is considered as high/low if it meets the criterion for observed values

Botulinum Toxin Antibodies

For the subset of subjects with body weight greater or equal to 21 kg, frequency tables will be presented for Screening V1 by category (Fluorescence Immuno Assay for antibodies (FIA-AB)/Hemi diaphragm assay (HDA)), treatment group, pre-treatment status (treatment-naïve/pre-treated, i.e. pre-treatment with any BTX for any indication).

Investigator’s Global Assessment of Tolerability

Frequency tables and descriptive statistics will be generated for the data collected at Final Visit V5 of the Main Period.

The following analyses will be performed for the OLEX data:

C-SSRS

For the sub-population of subjects enrolled after amendment 1.0 approval and of respective age and cognitive state the following analysis will be performed. Descriptive frequency tables will be displayed for total sub-population and by MP treatment group. The number of subjects who experience any suicidal ideation, suicidal behavior, or self-injurious behavior without suicidal intent at least once at any visit of the OLEX will be tabulated. Statistical evaluation of the data will be performed according to Table 1 of the Columbia–Suicide Severity Rating Scale Scoring and Data Analysis Guide Version 2.0 (Finalized February 2013) [Nilsson 2013 (5)]. Further C-SSRS data such as intensity of ideation and lethality data will only be listed.

Laboratory data

Descriptive statistics for absolute values at the Injection Visit V6 and the End of Study Visit (V17) and changes from Screening V1 to V6 and to V17 will be given for continuous variables.

The number of subjects with lowered, normal, or raised values compared to normal range as shift tables from Screening V1 vs. V6 and V1 vs. V17. Laboratory parameters will be sorted by predefined categories (e.g., hematology, differential count, and chemistry).

Laboratory data, unscheduled and doubly performed laboratory data will be listed individually. For additionally performed laboratory measurements of certain subjects on other visit dates or of other laboratory parameters than planned no descriptive statistics will be created. If subjects have additional laboratory examinations during screening examination, only the last sample before treatment start will be used. The first valid value for a post-baseline visit is analyzed.

Vital signs, body weight, height, and BMI

The individual blood pressure, heart rate, body weight, height, and BMI data will be listed and summarised (n, mean, standard deviation, minimum, 1st quartile, median, 3rd quartile and maximum) at each time point. Descriptive statistics will be given for absolute values and changes from baseline V2.

Frequencies of subjects with lowered, normal, or raised values will be displayed as shift tables from Baseline V2 vs. all available OLEX period visits.

Botulinum Toxin Antibodies

For the subset of subjects with body weight greater or equal to 21 kg, frequency tables and shift tables for Screening vs. End of Study Visit (V17) will be presented by category (Fluorescence Immuno Assay for antibodies (FIA-AB)/Hemi diaphragm assay (HDA)), treatment group, pre-treatment status (treatment-naïve/pre-treated, i.e. pre-treatment with any BTX for any indication).

Investigator's Global Assessment of Tolerability

Frequency tables and descriptive statistics will be generated for the data collected at Day 99 (Week 14) of all OLEX cycles.

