### **AESI monitoring and Safety Visit**

To monitor potential spread of toxin, the subject (if applicable) and/or parent(s) or caregivers (if applicable) will be actively questioned for the occurrence of AESIs at each visit or Telephone Contact [TC] starting with Baseline Visit of MP (V2). If a TC identifies an (S)AE/AESI that needs confirmation or treatment (e.g., respiratory disorder, dyspnoea, aspiration, dysphagia, speech disorder, dysphonia, other signs of bulbar palsy or botulism), the investigator must schedule a Safety Visit [SV] in addition to scheduled visits as soon as possible after the Telephone Contact. SV are unscheduled extra visits for assessment of (S)AE/AESIs only.

[figure not shown]
If a subject withdraws from participation during the study at any point of time, every attempt should be made to conduct the assessments foreseen for the End of Study Visit (V17).

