## 9 STUDY ASSESSMENTS AND VISIT SCHEDULE

### 9.1 Assessments

The following efficacy and safety assessments will be performed during this double-blind, randomized, parallel-group three arm dose-response study. The assessments on the AS used as efficacy variables will be performed by trained investigators only (see [Sections 9.1.1.1](#) and [9.1.1.2](#)). The assessment of AS must be performed after the assessment of GICSSs at week 4 of all treatment cycles of MP and OLEX. On days of injection visits, all assessments have to be performed prior to injection treatments. For standardization of laboratory test results, a central laboratory will analyze blood samples in this multi-center study.

An overall description of the study plan is provided in [Section 6.1](#) and in the Flow Chart in [Section 6.1.2](#). The time schedule of assessments is detailed in [Section 9.2](#). A tabular overview of study assessments is given in [Table 16](#) and [Table 17](#).

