6.5.3 Other Safety Variables

Other safety variables of the MP comprise:

- Investigator's Global Assessment of Tolerability at the Final Visit of MP V5 (In the definition of this variable the visit number was added.)
- Vital signs (blood pressure, heart rate) at all visits of MP
- Body Mass Index (BMI), weight and height at Screening V1, Baseline Injection Visit V2, at the Final Visit of MP V5
- Clinical chemistry, differential count and hematology at Screening V1
- Occurrence of antibodies against BoNT-A in subjects ≥ 21 kg BW at Screening V1
- Number of subjects with suicidal ideation, suicidal behavior, and self-injurious behavior without suicidal intent based on the Columbia-Suicide Severity Rating Scale (C-SSRS) This scale is used to assess suicidality prospectively in this clinical study at baseline and all post-baseline visits of the MP.

Other safety variables of the OLEX comprise:

- Investigator's Global Assessment of Tolerability at Day 99 (Week 14) of all OLEX cycles, i.e. at End of Cycle Visit (V9, V13) and at End of Study Visit (V17). In the definition of this variable the visit numbers were added.
- Vital signs (blood pressure, heart rate) at all visits of OLEX period (V6, V7, ..., V17). In the definition of this variable the visit numbers were added.
- BMI, weight and height at all Injection Visits of OLEX (V6, V10 and V14) and at the End of Study Visit (V17). If V5 and V6 will be performed at the same day, BMI, weight and height can be transferred from V5 to V6.
- Clinical chemistry, differential count and hematology at the Injection Visit V6 of OLEX and the End of Study Visit (V17).
- Occurrence of antibodies against BoNT-A in subjects ≥ 21 kg BW at the End of Study Visit (V17). In the definition of this variable the visit numbers were added.
- Number of subjects with suicidal ideation, suicidal behavior, and self-injurious behavior without suicidal intent based on the Columbia-Suicide Severity Rating Scale (C-SSRS) This scale is used to assess suicidality prospectively at all OLEX visits.

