7.5 Safety Variables

All safety analyses of the MP will be performed on the SES of the MP. All safety analyses of the OLEX Period will be performed on the SES of the OLEX period. Analyses will be based on both, total population and by Main Period treatment group (high, mid, low). For this purpose the Main Period treatment group as treated instead of as randomized will be used. In the unlikely case that a subject has received mid or low dose instead of the planned high dose during the OLEX Period, he/she will be analyzed in total group of the OLEX tables together with all other subjects with the correct high dose treatment.

For safety variables the last measurement before start of treatment is defined as baseline value.

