7.5.2 Secondary Safety Variables

Adverse events

AEs will be coded according to the Medical Dictionary for Regulatory Activities (MedDRA, version 21.0). For MP, only treatment emergent adverse events (TEAEs) of the MP will be analyzed, which are defined as AEs with onset or worsening on or after date and time of the first MP administration and before date and time of the first OLEX administration at V6. For subjects who do not receive an OLEX administration all AEs with onset or worsening on or after date and time of the first MP administration will be considered as TEAEs of MP. TEAEs of the OLEX are defined as AEs with onset or worsening at or after date and time of the first OLEX administration at V6. TEAEs will be allocated to an injection cycle x in the OLEX Period, if adverse events has onset or worsening on or after injection x and before injection x+1 (if applicable). TEAEs of the OLEX will be analyzed in total and per treatment cycle. Additionally TEAEs of the MP and the OLEX period will be displayed together in total.

Only TEAEs will be analyzed. Non-TEAEs will only be listed.

If an AE worsens between start and end of this AE it will be considered as new AE starting with the date of the worsening. In this case the imputation of end dates within episodes of the

same AE will be done by setting the end date/end time to start date/start time of the consecutive worsening record.

In detail missing or partially missing start and stop dates of an AE will be imputed as follows for the calculation of the duration of an AE:

- if start time is missing and start date is given and not equal to date of an injection visit, set start time to 00:00, else if start date is equal to date of an injection visit set start time to time of injection, if given (else 00:00)
- if start date/time is completely missing and end date is before first exposure in the MP: no imputation
- if start date/time is (partially) missing and end date after or equal first exposure in the MP or missing:
 - only start day is missing, but start month and start year same as an injection visit: set start day and start time to day and time of this injection visit, else set start day to 1 and start time to 00:00
 - start day and start month are missing, but start year is the same as year of first exposure in the MP: set start day, start month, start time to day, month, time of first exposure in the MP, else set start day and start month to 1 and start time to 00:00

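### Post-dose laboratory values of subjects treated only in the Main Period are listed but never summarised, because the MP laboratory summary stops at Screening and the V6 and V17 summaries use the OLEX safety set

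*SAP*

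**What the plan says.** For MP laboratory data, SAP 7.5.3 specifies: "Descriptive statistics for absolute values at Screening V1 will be given for continuous variables". It then adds: "No post-baseline laboratory data is planned for the MP". The same paragraphs say that all laboratory data, including unscheduled and repeated samples, are listed individually, and that measurements on visit dates other than those planned receive no descriptive statistics.

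For OLEX, the same section provides "Descriptive statistics for absolute values at the Injection Visit V6 and the End of Study Visit (V17) and changes from Screening V1 to V6". The change at V17 is included too, with shift tables against the normal range. SAP 6.5.3 likewise places the V6 and V17 laboratory variables under OLEX. SAP 7.5 fixes the population: "All safety analyses of the OLEX Period will be performed on the SES of the OLEX period". SAP section 5 defines that set as subjects who received study medication at least once in OLEX. Safety tables are shown in total and by MP dose group as treated (SAP 7.5).

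The protocol draws chemistry and haematology at V1, V6 and V17 (9.1.2.1.1). On timing, protocol 9.1 states: "On days of injection visits, all assessments have to be performed prior to injection treatments". For subjects who withdraw at any point, protocol 6.1 asks sites to try to carry out the End of Study (V17) assessments, and protocol 7.3.1 says an End of Study Visit should follow discontinuation for safety reasons.

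**The concern.** The V1-to-V6 change is the only scheduled laboratory change whose exposure is limited to the randomised dose. After V6 every continuing subject has also received open-label high-dose treatment. A by-dose description of laboratory safety would naturally cover everyone dosed in MP. Under the SAP it covers only subjects who went on to an OLEX injection, so membership depends on events after randomisation. Those who leave include subjects stopped for adverse events, and subjects with no need for reinjection by week 16, which may itself vary with dose.

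The SAP is also not uniform about where MP ends. For adverse events (7.5.2), MP runs until "before date and time of the first OLEX administration at V6". A V6 blood sample taken before the injection lies inside that window, but its results are reported as OLEX data.

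Finally, protocol 12.4.5 and the opening of SAP 7.5.3 both promise laboratory values and changes from baseline. Protocol 12.3.5.3 says these variables are determined for MP and for all OLEX cycles. The MP part of SAP 7.5.3 gives no change from baseline, and SAP section 8 does not record this as a change to the planned analyses.

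**Working it through.** The plan gives no figure to reproduce, so the check is to follow each laboratory sample to its summary table.

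| Sample | Exposure when drawn | Period assigned by SAP | Safety set of the summary | Outcome |
|---|---|---|---|---|
| V1 | none | MP | SES of MP | summarised for all dosed subjects |
| V6, followed by injection | blinded MP dose only | OLEX | SES of OLEX | summarised by MP dose |
| V6, no injection follows | blinded MP dose only | OLEX | subject not in SES of OLEX | listed only |
| Early End of Study after MP, no OLEX dose | blinded MP dose only | OLEX (as V17), or off-schedule | subject not in SES of OLEX | listed only |
| V17 after OLEX | MP dose plus open-label high dose | OLEX | SES of OLEX | summarised by MP dose |

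Sources: sampling visits from protocol 9.1.2.1.1; timing relative to injection from protocol 9.1; period assignment from SAP 6.5.3 and 7.5.3; safety sets from SAP 5 and 7.5; listing and off-schedule rules from SAP 7.5.3.

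Two conditions together produce the two listed-only rows: the MP summary stops at V1, and the summaries that hold post-dose values require an OLEX injection. Assigning V6 to OLEX adds to the gap only in the third row, for subjects sampled at V6 and then not injected. For subjects who leave without a V6 sample, that assignment makes no difference.

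**Scale.** The documents give no rate of stopping by the end of MP. The only attrition figure is the 3% drop-out at the time of the primary assessment, taken from comparable placebo-controlled studies (SAP section 4). With 344 planned subjects, all assumed dosed in MP, the number affected is at most 344 × the proportion not treated in OLEX:

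- 3%: 344 × 0.03 = 10.3, about 10
- 10%: 344 × 0.10 = 34.4, about 34
- 15%: 344 × 0.15 = 51.6, about 52

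The 10% and 15% are assumptions. Each count is an upper bound because it treats every non-continuer as having a post-dose sample. The synopsis (Duration of treatment per subject) says subjects with no need for reinjection by week 16 finish after the final MP visit, V5, and protocol 9.1.2.1.1 schedules no blood draw at V5. Protocol 7.2.1 describes the same subjects as withdrawn, which would bring in the End of Study assessments. Whether they are sampled is therefore unclear. In pregnancy no blood is drawn.

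**The case against.** The case for leaving the SAP as it stands has several parts.

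- **The sentence follows the protocol.** Blood is scheduled only at V1, V6 and V17, and protocol 12.3.5.3 itself labels V6 an OLEX injection visit. A reader might infer that the SAP denies that post-dose data exist. It says only that none are planned for MP. This stands.
- **The results are not lost.** A reader might infer that laboratory findings in subjects who leave disappear from safety reporting. They do not. V1 values are in the MP summary, post-dose values are listed, and SAP 7.5.3 screens laboratory data for individual notable values. Protocol 9.1.2.1.1 has relevant abnormalities recorded as adverse events. For subjects with no OLEX dose, SAP 7.5.2 counts every event from the first MP dose onward as an MP TEAE, tabulated by dose as treated. This stands. Even so, a listing gives no comparison by dose, and recording an abnormality as an adverse event depends on the investigator's judgement.
- **The V6 label hides nothing for continuers.** Their V1-to-V6 changes and shifts are shown by MP dose group. This stands, and it means the V6 label is not the main cause of the gap.
- **Samples may not exist.** Early End of Study sampling is to be attempted, not guaranteed, and no table can recover a sample never drawn. This stands and limits the size.
- **A pooled last value mixes times.** V6 falls about 12 to 16 weeks after dosing, whereas an early withdrawal sample may come at any time. This stands as a drawback of the fix. Reporting time since dosing makes it visible.

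None of this supplies a summary of post-dose laboratory values for subjects treated only in MP.

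**Conclusion.** The point holds as a gap in descriptive reporting. In the SAP text, post-dose laboratory values of subjects treated only in MP are, where collected, listed but not summarised. The laboratory change that isolates the blinded dose is summarised by MP dose only in those re-injected. On assumed non-continuation of 3% to 15%, at most about 10 to 52 of 344 subjects are affected; the true number is lower if early-exit samples were not taken.

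It would go too far to call this a biased test of laboratory safety. The laboratory analysis is descriptive, no dose comparison is tested, and leaving for lack of need for reinjection is a planned exit. The documents also do not show how those who leave differ from those who stay.

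The conclusion rests on the body of the SAP. Its list of tables (Appendix 1) and the protocol's activity schedules (Tables 16 and 17) were not in the text reviewed, so a table that closes the gap could exist there. The importance is low, but the change is cheap.

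**What to change.** In the MP part of SAP 7.5.3, replace the sentence that no post-baseline laboratory data is planned with the following:

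- Descriptive changes and shift tables from V1 to the last available laboratory value before any OLEX injection. That is the pre-injection V6 value, or the early End of Study value for subjects who leave in or after MP.
- Population: SES of the MP, by dose group as treated and in total.
- Alongside, by dose group: the number of subjects without a post-dose sample, and the time from MP injection to the sample.

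Align SAP 6.5.3 (MP list) and record the addition in section 8. The cut-off then matches the MP boundary already used for adverse events in 7.5.2, and the population matches 7.5. The existing OLEX tables can stay.

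The cost is one more set of descriptive tables. No sampling is needed beyond what the protocol already seeks, and no confirmatory test changes. The drawback is that sampling times will differ between continuers and early leavers, so the table must be read with the reported time since dosing.
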